10.7. Laboratory Abnormalities

Clinical labs will be analyzed by a central laboratory. Labs to be drawn during the study include serum chemistries, a hematology panel, and urinalysis. On-site urine pregnancy testing is performed at each visit for women of child-bearing potential; positive tests are confirmed with a serum pregnancy test. For post-menopausal women less than 60 years of age, a serum FSH will be done at the screening visit only. Screening pregnancy tests must be negative prior to study entry. If any local laboratory is used, the investigator must obtain verification that it meets the standards for quality and consistency set by the College of American Pathologists.

Clinical laboratory reports must be reviewed by a physician for out-of-range values within 24 hours of receipt. Out-of-range values will be evaluated using the following notations:

- NS: Not clinically significant
- LE: Laboratory Error
- PT: Subject abnormal; relates to the subject's usual state of health
- CS: Clinically Significant. This value cannot be explained by any of the other flags.

By definition a lab value flagged as "CS" must be entered on the adverse clinical laboratory event page in the CRF. A laboratory test flagged "CS" must be repeated as soon as possible. The investigator may use his/her own judgment as to whether the abnormal finding is sufficient reason to immediately withdraw the subject from the study.

If a laboratory value is considered to be serious and life-threatening the subject should be immediately discontinued from the study and appropriate therapy started. Refer to [Section 10.9](#) through [Section 10.12](#) for the definition of a serious adverse event and related terms, and for details on reporting a serious adverse event.

10.8. Adverse Event Assessment and Recording

All adverse events, exacerbations of concomitant illnesses, or events known to be related to underlying disease processes or concomitant medications are to be recorded on the CRF throughout the study. (Procedures such as surgery should not be recorded as adverse events. However, the medical condition for which the procedure was performed should be reported if it meets the definition of adverse event.) If a pre-existing condition worsens on study, the date on which the exacerbation began should be recorded. Onset dates for study treatment-related adverse events must be on or after the date of initial study treatment use. The need to record an adverse event on the CRF is not dependent on whether the adverse event is associated with the use of the study medication. In order to avoid vague, ambiguous or colloquial expressions, the adverse event should be recorded in standard medical terminology.

Adverse event recording will include the date of onset, severity, duration, whether or not the study medication was discontinued, or its dosage changed because of the event, the treatment given and the outcome. The investigator must also assess whether the event was related to the study medication, concurrent drug therapy, underlying disease, a combination of these factors, or if it is unknown. Subjects with an adverse event should be carefully followed to determine outcome.

The investigator will use the National Cancer Institute (NCI) definitions to grade the severity of the event. There is a distinction between the severity and the seriousness of an adverse event. Severe is a measurement of intensity, thus a severe reaction is not necessarily a serious adverse event. For example, a headache may be severe in intensity, but would not be serious unless it met one of the criteria for serious adverse events listed previously.

Table 3: Adverse Event Grading Terms

Grade 1: **Mild**; asymptomatic or mild symptoms; clinical or diagnostic observations only; intervention not indicated

Grade 2: **Moderate**; minimal, local, or non-invasive intervention indicated; limiting age-appropriate ADL

Grade 3: **Severe** or medically significant but not immediately life-threatening; hospitalization or prolongation of hospitalization indicated; disabling; limiting self-care ADL.

Grade 4: **Life-threatening** consequences; urgent intervention indicated.

Grade 5: **Death**

The relationship or association of the study medication in causing or contributing to the adverse event will be characterized as defined below:

Table 4: Adverse Event Relatedness Terms

Not related: Evidence indicates no plausible direct relationship to the study medication.

Remote: Suggests other conditions are reasonably likely to account for the event including concurrent illness, progression or expression of the disease state, or reaction to concurrent medication.

Possible: Suggests that the association of the event with the study medication is unknown; however, the adverse event is not reasonably supported by other conditions.

Probable: Suggests that a reasonable temporal sequence of the event with medication administration exists and, based upon the investigator's clinical experience, the association of the event with study medication seems likely.

Definite: Suggests that based upon the investigator's experience, the association of the event with the study medication seems very certain.

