10.11. Notification of Serious Adverse Events

Under IND regulations, 21 CFR Part 312.64, investigators must immediately report to the Sponsor any serious adverse event, whether or not considered drug related, including those listed in the protocol or investigator brochure and must include an assessment of whether there is a reasonable possibility that the drug caused the event.

The Sponsor must be notified as detailed in [Section 10.12](#), "Reporting a Serious Adverse Event." The Sponsor, in turn, will report all serious adverse events to regulatory agencies as required. In addition to the serious adverse events described in [Section 10.10](#), other events that in the investigator's opinion suggest a significant hazard, contraindication, or precaution should be considered serious. This includes, but is not limited to, blood dyscrasias, endocrine disturbances, hemorrhage from any site, or severe skin disorder. Additional examples are intensive treatment in an emergency room or at home for allergic bronchospasm, blood dyscrasias or convulsions that do not result in hospitalization, and development of drug dependency or drug abuse. Hospitalization for elective surgery is not considered an SAE. In addition, pregnancy is not an SAE, but is reportable and must be reported per IND regulations and timelines, 21 CFR Part 312.64, on the SAE reporting form and submitted to the sponsor.

Subjects who experience an SAE must be given appropriate examinations and treatment. The investigator must provide written information to the sponsor as soon as possible.

When an investigator is in doubt when to report an event, the investigator should err on the side of caution and contact the Sponsor.

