10.15. Stopping Rules

It is anticipated that no more than 2 subjects out of 50 (4.0 %) will have an AE of Grade 4 or Grade 5 that is at least possibly related to ENT-01 in this Study. Should there be more than 2 subjects with an AE grade 4 or 5 that is at least possibly related to ENT-01 in the cohort of subjects, the study will be put on an immediate clinical hold. Safety Monitoring processes are identified in [Section 10.14](#).

In addition, individual safety stopping criteria will include:

- Reaching DLT before a prokinetic effect
- Serious Adverse Event at least possibly attributable to ENT-01.
- Having a non-DLT gastrointestinal adverse event > grade 3 within 24 hours of taking ENT-01 that is at least possibly attributable to ENT-01
- A fall in systolic blood pressure to < 80 mm Hg upon rising from lying to sitting or standing
- A fall in diastolic blood pressure to < 40 mm Hg upon rising from lying to sitting or standing

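### Table 4 keeps uncertain events with another reasonable cause out of Possible, which can lower the count for the study hold and for two of the five individual stopping criteria

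*Combined protocol and SAP*

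**What the plan says.** Section 10.8, Table 4, has five classes of relatedness. Its introductory sentence covers both causation by the study medication and contribution from it. Three rows matter here:

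- **Remote**: "Suggests other conditions are reasonably likely to account for the event including concurrent illness, progression or expression of the disease state". The row also takes in reactions to other drugs.
- **Possible** is defined as: "Suggests that the association of the event with the study medication is unknown; however, the adverse event is not reasonably supported by other conditions".
- For **Probable**, the table asks for a reasonable time sequence and, on the investigator's experience, "the association of the event with study medication seems likely". Nothing is said about other causes.

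Earlier in Section 10.8 the investigator must judge whether an event was due to the trial drug, to other drug treatment, or to "underlying disease, a combination of these factors, or if it is unknown". For serious events, Section 10.11 says the report "must include an assessment of whether there is a reasonable possibility that the drug caused the event".

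The class then feeds the safety triggers. Section 10.15, like Section 2.1, imposes a clinical hold: "Should there be more than 2 subjects with an AE grade 4 or 5 that is at least possibly related to ENT-01". Two of the five individual criteria in Section 10.15 also depend on it. One is a "Serious Adverse Event at least possibly attributable to ENT-01"; the other is a non-DLT gastrointestinal event above grade 3 with the same attribution test. Section 11.3 separately summarizes AEs related to study medication.

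**The concern.** A causality scale should rise in one direction, each step asking for more evidence against the drug. Here the weaker class, Possible, requires that other conditions do not reasonably support the event, and the stronger class, Probable, does not. The commonest difficult case is one where the drug might have done it, something else might have, and nobody can say which. Table 4 bars that case from Possible.

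This matters because the trial is single-arm and safety is a primary objective. No control rate is available to show an excess of events that investigators attributed to the disease or to other drugs. The hold acts on three subjects, so moving even one or two events below Possible can decide whether it is reached. Subjects have Parkinson's disease and may stay on many concomitant drugs (Section 7), so disease expression and drug reactions, both named in the Remote row, will often be available as explanations.

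**Working it through.** **Step 1. The definitions applied to each kind of event**

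| Drug association | Other condition | Class under Table 4 | Counted as at least possible? |
|---|---|---|---|
| Judged likely or very certain | Present or absent | Probable or Definite | Yes |
| Unknown | Does not reasonably support the event | Possible | Yes |
| Unknown | Reasonably likely to account for the event | Remote | No |
| Unknown | Reasonably supports the event but falls short of reasonably likely | Barred from Possible; no class clearly fits | Not clearly |
| No plausible direct relationship | Any | Not related | No |

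The third and fourth rows are the problem. Such an event could be called a combination, or unknown, under the text of Section 10.8, and could meet the reasonable-possibility test of Section 10.11, yet not count under Section 10.15.

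**Step 2. Direction**

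Suppose another reasonable cause did not by itself exclude Possible. Some events in rows three and four would move up to Possible, and no event now counted would move down. Against that reading, the present wording can only lower the count.

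**Step 3. The plan's own figures**

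- Section 11.7: the chance of at least one event at a 5% rate in 50 patients is 1 − 0.95^50 = 1 − 0.0769 = 0.923. The stated 92% reproduces.
- Section 10.15 anticipates "no more than 2 subjects out of 50 (4.0 %) will have an AE of Grade 4 or Grade 5" at least possibly related to ENT-01: 2/50 = 4.0%. This agrees.

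**Step 4. Illustration of the effect on the hold**

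Inputs: n = 50 (Section 11.7); hold at 3 or more counted subjects (Section 10.15). Assumed, because the documents give neither: p, the true proportion of subjects with a drug-caused grade 4 or 5 event, and s, the share of those rated Possible or higher. Subjects are treated as independent, and q = p × s.

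P(hold) = 1 − [(1−q)^50 + 50q(1−q)^49 + 1225q²(1−q)^48]

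- p = 4%, s = 100%, q = 0.04: 1 − (0.130 + 0.271 + 0.276) = 0.323
- p = 4%, s = 50%, q = 0.02: 1 − (0.364 + 0.372 + 0.186) = 0.078
- p = 10%, s = 100%, q = 0.10: 1 − (0.005 + 0.029 + 0.078) = 0.888
- p = 10%, s = 50%, q = 0.05: 1 − (0.077 + 0.202 + 0.261) = 0.459

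The range (bracketed terms above are rounded; results come from unrounded values):

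| True rate p | s = 100% | s = 75% | s = 50% | s = 25% |
|---|---|---|---|---|
| 4% | 0.323 | 0.189 | 0.078 | 0.014 |
| 5% | 0.459 | 0.289 | 0.129 | 0.025 |
| 8% | 0.774 | 0.584 | 0.323 | 0.078 |
| 10% | 0.888 | 0.734 | 0.459 | 0.129 |
| 15% | 0.986 | 0.931 | 0.734 | 0.289 |

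**The case against.** The strongest reply is that the effect is narrow and well backed up.

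- **Two-cause events are not all lost.** A reader might infer that any event with a plausible alternative cause becomes Remote. Table 4 does not say that. Remote needs the other condition to be reasonably likely to account for the event, and Probable and Definite stay open whatever else is present. This stands, and it limits the point to events whose link to the drug is uncertain.
- **Most safety machinery ignores relatedness.** A reader might infer that the stopping rules as a whole undercount. Three of the five individual criteria in Section 10.15 (DLT before a prokinetic effect, and the systolic and diastolic falls) carry no causality rating, and neither do the DLT definitions in Section 10.4. All AEs are recorded (Section 10.8), all SAEs are reported within 24 hours (Section 10.12), the TEAE, SAE and grade 3 or higher summaries are not filtered by cause (Section 11.3), and a DSMB monitors safety (Section 10.14). This stands too. It does not repair the hold, which is tied to the rating, and Section 10.14 gives no alternative threshold.
- **Grade 4 and 5 events already get the Section 10.11 assessment**, since life-threatening and fatal events are serious under Section 10.9. True, but the hold is not stated in those terms, so one event could pass that assessment and remain uncounted.
- **The background examples prove nothing.** A reader might cite the gastrointestinal bleed, the dizziness on an alpha-blocker and the falls in Section 1 as harms lost in this way. The documents do not show that those studies used Table 4. The bleed came after the drug was stopped and was called unrelated; the patient with dizziness was withdrawn anyway; the falls have no stated class. They show only that competing explanations arise.
- **A wider Possible has its own cost.** With no control arm, background events would count more readily. At a counted rate of 5%, whatever the cause, the table gives a 0.459 chance of a hold. This is a real trade-off.

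**Conclusion.** The point holds in a limited form. Table 4 is internally out of order and does not fit its own introduction, the combination wording in Section 10.8, or Section 10.11. The result is a one-directional risk: the count can be lowered for the hold, for the SAE and non-DLT gastrointestinal individual criteria, and for the related-AE summary. Nothing else in the safety plan is affected.

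The size is not known. The halving from 0.888 to 0.459 at a 10% rate might be read as an estimate of lost protection. It is not one: 10% is two and a half times the 4% that the plan anticipates, and the half share is chosen for illustration. At 4% the hold has only a 0.323 chance of being reached even with every event counted, falling to 0.078 at the same share. The documents support the direction, and support calling it a risk. They do not support a statement that harms will be undercounted.

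It is worth correcting because the trigger is only three subjects and the correction is small.

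**What to change.** Reconcile the Possible and Remote rows of Table 4 with the text of Section 10.8 and with Section 10.11, so that:

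1. another reasonable cause does not by itself exclude Possible;
2. events with two reasonable causes, and events the investigator records as a combination or as unknown, have a stated class;
3. no event falls between Remote and Possible.

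The sponsor should then confirm that Sections 2.1 and 10.15 and the related-AE summary in Section 11.3 all use the reconciled scale. The hold threshold, the stopping criteria and the attributions that count toward them remain the sponsor's decision.

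The cost is one amended table and site retraining. The related-AE rate would look somewhat higher, and without a control arm there is some added chance that background events count toward the hold.

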10.9. Reporting Requirements

Any adverse event, including both observed or volunteered problems, complaints, or symptoms that begins any time between the signing of the consent and within 30 days after the end of study participation are to be recorded briefly on the appropriate CRF and in detail in the source documents. A check list of adverse events may not be used during this study.

The following are specific definitions that are relevant to meeting your reporting obligations and which are included in the FDA Regulations, 21 CFR Part 312.32, and International Conference on Harmonization of Technical Requirements for Registration of Pharmaceuticals for Human Use (ICH) Guidelines:

Adverse Event: Any untoward medical occurrence in a subject administered a pharmaceutical product and which does not necessarily have to have a causal relationship with this treatment. An adverse event can be any unfavorable sign (including an abnormal laboratory finding), symptom, or disease temporally associated with the use of the investigational drug, whether or not considered related to the investigational drug.

Serious Adverse Event: An untoward event or reaction that at any dose:

- results in death
- is life-threatening
- requires in-patient hospitalization
- prolongs existing hospitalization
- results in permanent or significant disability or incapacity
- is a congenital anomaly/birth defect
- requires intervention to prevent permanent impairment/damage

Life-threatening: An event which a subject was at risk of death at the time of event.

10.10. Serious Adverse Events

Adverse events (AEs) and serious adverse events (SAEs) will be collected from signing of informed consent until the follow-up contact. Medical occurrences that began prior to the start of study treatment, but after obtaining informed consent were recorded on the Medical History/Current Medical Conditions CRF. The investigator or site staff will be responsible for the detection and documentation of events meeting the criteria and definition of an adverse event or serious adverse event, as provided in the study protocol.

However, any SAEs assessed as related to study participation (e.g., dosing, protocol mandated procedures, invasive tests, or change in existing therapy) or related to a concomitant medication will be recorded from the time a subject consent to participate in the study up to and including any follow-up contact.

In the event of an AE or SAE, it will be the responsibility of the Investigator to review all documentation (e.g., hospital progress notes, laboratory, and diagnostics reports) relative to the event and attempt to establish a diagnosis of the event based on signs, symptoms, and other clinical information. The diagnosis was to be documented as the adverse event or serious adverse event and not the individual's signs/symptoms. Once an Investigator becomes aware that a SAE has occurred in a study subject, they are to report the information to Enterin within 24hrs and provide an assessment of causality.

10.11. Notification of Serious Adverse Events

Under IND regulations, 21 CFR Part 312.64, investigators must immediately report to the Sponsor any serious adverse event, whether or not considered drug related, including those listed in the protocol or investigator brochure and must include an assessment of whether there is a reasonable possibility that the drug caused the event.

The Sponsor must be notified as detailed in [Section 10.12](#), "Reporting a Serious Adverse Event." The Sponsor, in turn, will report all serious adverse events to regulatory agencies as required. In addition to the serious adverse events described in [Section 10.10](#), other events that in the investigator's opinion suggest a significant hazard, contraindication, or precaution should be considered serious. This includes, but is not limited to, blood dyscrasias, endocrine disturbances, hemorrhage from any site, or severe skin disorder. Additional examples are intensive treatment in an emergency room or at home for allergic bronchospasm, blood dyscrasias or convulsions that do not result in hospitalization, and development of drug dependency or drug abuse. Hospitalization for elective surgery is not considered an SAE. In addition, pregnancy is not an SAE, but is reportable and must be reported per IND regulations and timelines, 21 CFR Part 312.64, on the SAE reporting form and submitted to the sponsor.

Subjects who experience an SAE must be given appropriate examinations and treatment. The investigator must provide written information to the sponsor as soon as possible.

When an investigator is in doubt when to report an event, the investigator should err on the side of caution and contact the Sponsor.

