The results of the study indicated that orally administered ENT-01 was safe and significantly improved bowel function and neurologic symptoms. Minimal systemic absorption suggests that improvements result from local stimulation of the ENS.

A randomized, placebo-controlled Phase 2b study (KARMET) of orally administered ENT-01 is currently being conducted in patients with PD and constipation. Dosing is daily, beginning at either 75 mg (baseline CSBM 1.0-3.0) or 150 mg (baseline CSBM 0-0.9) and escalating by 25 mg every 3 days until pro-kinetic effect or a maximum dose of 250 mg. Total treatment duration is 25 days.

A top-line data cut of the first 57 patients (an extension study is currently being performed) showed that ENT-01 achieved the primary efficacy endpoint in the treatment of constipation, with CSBM frequency increasing from 1.0 at baseline to 4.8 at the end of the fixed dosing period. Six patients exhibited hallucinations and/or delusions at the beginning of the study. These neurological symptoms disappeared or improved in 5 subjects randomized to ENT-01 but not in the 1 placebo patient. The dose required for improvement or disappearance of these neurological symptoms was patient specific. There were also improvements in other CNS parameters, including motor symptoms and memory.

Many of the AE were confined to the GI tract and were mild to moderate. Common adverse events included nausea in 10/53 (18.3%), diarrhea in 4/53 (7.4%), and abdominal pain in 4/53 (7.4%). There were 4 SAEs, 2 hospitalizations for joint replacement (1 patient on ENT-01 and 1 on placebo), 1 hospitalization for cholecystectomy and 1 for diuretic induced hypokalemia with weakness. Two of the 6 falls in the ENT-01 group occurred during the treatment period, the other

4 did not. In both cases the patient had a prior history of falls. The study is on-going, and a study report will be filed at the conclusion of the study.

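### The unqualified elective-surgery exclusion in section 10.11 can remove SAE status from a condition that begins or worsens on study, in conflict with section 10.9

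*Combined protocol and SAP*

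**What the plan says.** Four parts of the protocol bear on how a surgical admission is classified.

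- **Section 10.9** defines a serious adverse event. One criterion is that the event "requires in-patient hospitalization". The definition there makes no exception for elective admissions.
- **Section 10.11** adds the exception: "Hospitalization for elective surgery is not considered an SAE". The protocol does not define elective. It does not limit the sentence to operations planned before consent, or to old conditions that have stayed the same.
- **Section 10.8** separates the operation from its cause. It says "Procedures such as surgery should not be recorded as adverse events", and then "However, the medical condition for which the procedure was performed should be reported if it meets the definition of adverse event". It adds: "If a pre-existing condition worsens on study, the date on which the exacerbation began should be recorded".
- **Section 10.15** lists among the individual stopping criteria a "Serious Adverse Event at least possibly attributable to ENT-01".

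Section 10.12 requires SAEs to be reported within 24 hours of the site learning of them, and section 11.3 lists SAEs among the summaries to be produced. Section 2.1 makes safety and tolerability a primary objective. For KARMET, the randomized study that supplies every subject, section 1 lists 4 SAEs. They include "2 hospitalizations for joint replacement (1 patient on ENT-01 and 1 on placebo), 1 hospitalization for cholecystectomy"; the fourth was an admission for hypokalemia.

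**The concern.** Section 10.8 draws the right distinction: the operation is not the event, the condition behind it is, and a worsening counts. Section 10.11 does not carry that distinction into the definition of seriousness. It excludes by type of admission, whatever the cause and whenever the condition arose.

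In a safety study the events of interest are those that begin or worsen after exposure. Section 1 names local gastrointestinal toxicity as the main safety concern. A gastrointestinal condition that appears on drug, is investigated, and is then treated by a scheduled operation is the kind of event for which serious status should not depend on how the admission was booked. There is time for this to happen: about 14 weeks of dosing plus a 6-week wash-out is 20 weeks, and section 10.9 records events for a further 30 days after participation ends.

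At stake are expedited reporting of such an event, its place in the SAE summary, and whether it meets the one individual criterion in 10.15 that depends on SAE status. With about 20 sites and no definition of elective, different sites could also classify the same event differently.

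**Working it through.** **1. The conflict, traced through one case.** Take a subject whose condition first appears, or clearly worsens, in week 5 of dosing and who is admitted in week 12 for a scheduled operation.

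| Section | Result for this case |
|---|---|
| 10.8 | The operation is not an AE; the condition, or its worsening, is |
| 10.9 | The AE led to in-patient admission, so it is serious |
| 10.11 | The admission was for elective surgery, so it is not an SAE |

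Sections 10.9 and 10.11 give opposite answers, and nothing in the protocol says which prevails.

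**2. What follows if 10.11 prevails.**

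- Lost: the 24-hour report (10.12), the entry in the SAE summary (11.3), and the 10.15 criterion for a related SAE.
- Kept: the AE record (10.8), the TEAE and related-AE summaries (11.3), and probably the summary of Grade 3 or higher events, because Table 3 names an indication for hospitalization among its Grade 3 descriptors.
- Unaffected: the study-level hold in 2.1 and 10.15, which counts subjects with related Grade 4 or 5 AEs and makes no use of SAE status.

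**3. The plan's own figure.** Section 11.7 gives a 92% chance of seeing at least one AE with a true rate of 5% in 50 patients. The check is 1 − 0.95^50 = 0.923, so the figure reproduces. It concerns AEs of any kind, and the exclusion in 10.11 does not change it.

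**4. How common such admissions might be.** The only data in the protocol are the KARMET SAEs in section 1: 2 joint replacements + 1 cholecystectomy + 1 hypokalemia = 4, so 3 of 4 (75%) are named by an operation. One joint replacement was on ENT-01 and one on placebo. The arm of the cholecystectomy is not given, so at most 2 of the 3 were on ENT-01.

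Whether any of the three was elective is not stated, so the full range has to be shown. Section 1 gives two possible denominators, 57 patients in the data cut and 53 in the AE percentages. The percentages below assume one SAE per patient.

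| Number assumed elective | SAEs left under 10.11 | Out of 57 | Out of 53 |
|---|---|---|---|
| 0 | 4 | 4/57 = 7.0% | 4/53 = 7.5% |
| 1 | 3 | 3/57 = 5.3% | 3/53 = 5.7% |
| 2 | 2 | 2/57 = 3.5% | 2/53 = 3.8% |
| 3 | 1 | 1/57 = 1.8% | 1/53 = 1.9% |

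The table shows how sensitive a small SAE count can be to this one sentence. It does not estimate what will happen in the present study.

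**The case against.** The strongest reply is that the sections can be read together. On that reading, 10.11 says only that being admitted for a planned operation is not in itself an SAE, while the condition behind it is still judged under 10.9. Section 10.11 also has two safeguards. It says that "other events that in the investigator's opinion suggest a significant hazard, contraindication, or precaution should be considered serious", and it tells an investigator in doubt to be cautious and call the sponsor. A condition may also be serious under another 10.9 criterion, such as disability or the need to prevent permanent impairment.

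Part of this stands. The event is not lost from the data, some such events would be serious on other grounds, and a careful site may well reach the right answer. But the harmonizing reading is not written down. The hazard clause depends on each investigator's opinion, and a flat exclusion leaves little doubt to act on. The safeguards reduce the problem without removing it.

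A second reply concerns KARMET, and it stands in full. A reader might infer that KARMET counted elective admissions as SAEs and that the two studies' counts therefore do not match. The documents do not support this: they give neither KARMET's SAE definition nor the elective status of the three operations. If the same sentence applied there and the admissions were not elective, there is no mismatch. Section 11.3 plans no pooling of SAEs with KARMET either; section 1 adds the two dosing periods together (18 weeks), not the events.

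**Conclusion.** The conflict between 10.9 and 10.11 is in the text and rests on no assumption. As written, a condition that begins or worsens on study and is treated by scheduled in-patient surgery can lose SAE status. SAEs can therefore be undercounted in a study with safety as a primary objective.

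The size in this study cannot be computed. The KARMET list shows that surgical admissions are plausible in this population. Between 0 and 3 of its 4 SAEs would be excluded by this rule, depending on an elective status that is not given. Comparability of SAE counts with KARMET is uncertain.

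Two further inferences go too far. One is that the SAE count is biased downward as an established fact; it is a risk that depends on such events occurring and on how sites read 10.11. The other is that the study's overall safety stop is weakened; it is not, because that rule uses related Grade 4 or 5 AEs. What can be lost is the SAE label and what depends on it, not the event.

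**What to change.** Reconcile 10.8, 10.9 and 10.11 by replacing the sentence in 10.11 with:

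*Hospitalization for elective surgery for a condition that existed before informed consent and has not worsened since is not an SAE, whenever the surgery was scheduled. Hospitalization for surgery for a condition that began or worsened after consent is classified under section 10.9.*

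Two features of this wording matter. The scheduling date plays no part, so an old, unchanged joint problem that comes up for surgery during the study is still excluded. The cut-off is consent rather than first dose, which matches the start of AE recording in 10.9 and leaves no gap for conditions that arise between the two. Section 10.10 places occurrences before treatment start on the medical history form and should be aligned at the same time. Carry the same rule into the SAE form guidance.

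If SAE counts are ever shown beside KARMET, state the SAE rule used in each study, or classify both by the same rule.

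The cost is a short protocol amendment and a note to sites. No visit, assessment or sample size changes. The downside is possibly a few more SAE reports and a slightly less favourable SAE count. This point takes no position on the stopping criteria in 10.15; it asks only that events be classified consistently before those criteria are applied.
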